6.2.4 Visit 05a (EGD +7 days) and Visit 06a (EGD day+7 days)	20
6.2.5 Visit 07 Day 365	20
6.3 Early Termination Visit (if needed).....	20
7 Statistical Considerations	21
8 Quality Control and Quality Assurance.....	22
9 Ethics/Protection of Human Subjects	23

9.1 Ethical Standard	23
9.2 Institutional Review Board	23
9.3 Informed Consent Process	23
9.4 Exclusion of Women, Minorities, and Children (Special Populations)	24
9.5 Subject Confidentiality	24
9.6 Future Use of Stored Specimens.....	24
10 Literature References	25

SUPPLEMENTS/APPENDICES

A: Study Schedule.....	28
B: Adverse Events Grading.....	30

Protocol Summary

Title:	Immunologic Responses to a Live Attenuated Oral Cholera Vaccine
Population:	50 subjects, 18 to 49 years old, who are in good health and meet the eligibility criteria
Clinical Sites:	The Hope Clinic of the Emory Vaccine Center, Emory University Emory GI Clinic/Ambulatory Surgery Center
Study Duration:	5 years
Subject Duration:	Approximately 13 months
Description of Agent:	One dose delivered orally of the FDA-approved live attenuated cholera vaccine (Vaxchora)

Objectives:

Primary:

- To evaluate the antibody response to the cholera vaccine in healthy subjects.

Secondary:

- To evaluate B cell responses in healthy subjects receiving the live attenuated cholera vaccine.
- To evaluate the safety and reactogenicity in healthy subjects receiving the live attenuated cholera vaccine.

Exploratory:

- To evaluate mucosal cell responses in a subset of the healthy subjects receiving the live attenuated cholera vaccine.

Endpoints:

Primary:

- Level of antibody titers at day 1 (pre-vaccination) and day 29 in serum.

Secondary:

- Levels of plasmablasts at days 1, 8 and 29

- Levels of activated B cells at days 1, 8 and 29
- Levels of memory B cells at days 1 and 29.
- Correlation between antibody titers and the level of plasmablasts, activated B cells, and memory B cells.
- Production and characterization of monoclonal antibodies against *V. cholerae* at day 8 in a subset of subjects.
- Solicited and unsolicited adverse events in healthy subjects receiving cholera vaccine at day 8 and day 29 respectively.
- Serious adverse events in healthy subjects receiving cholera vaccine for the duration of the study.

Exploratory:

- Levels of plasma cells, activated B cells and T cells in small intestinal biopsy samples at day 29 (n=15) or day 90 (n=5).
- Correlation between systemic and mucosal immune responses.
- Production and characterization of monoclonal antibodies against *V. cholerae* from a protected mucosal site.
- Levels of antibody titers at days 90 and 365.
- Levels of plasmablasts at days 11 and 15 in a subset of subjects.
- Levels of activated B cells at days 11 and 15 in a subset of subjects.
- Levels of T cells at days 1 and 29 in a subset of subjects.

KEY ROLES

Principal Investigator:	[name], FIDSA Division of Infectious Diseases Emory University The Hope Clinic of the Emory Vaccine Center [REDACTED]
Co-Principal Investigator:	[name] Division of Digestive Diseases, Emory University School of Medicine, [REDACTED]
Co-investigator/ Research Project Principal Investigator:	[name] Department of Microbiology and Immunology, School of Medicine, Emory University, [REDACTED] [REDACTED]

Institution: Emory University

1 BACKGROUND INFORMATION AND SCIENTIFIC RATIONALE

1.1 Background Information

Vibrio cholerae causes an acute diarrheal disease responsible for more than 100,000 deaths and affects an estimated 3 to 5 million people annually [1-3]. Recent epidemics in Haiti and Africa illustrate the continued reach of this pathogen [4]. Across the globe, one billion people lack access to safe drinking water and are vulnerable to cholera. The increasing disease burden, and emergence of more virulent strains, suggest that more aggressive approaches to preventing cholera are needed [5-7]. This includes renewed efforts to understand the mechanism of protective immunity against cholera and to improve the protective efficacy of current cholera vaccines.

V. cholerae infection and the need for improved vaccines. *V. cholerae* is a non-invasive pathogen, and thus represents an excellent model to study the induction and maintenance of mucosal immunity. *V. cholerae* colonizes the surface of the small intestine and expresses cholera toxin (CT). The enzymatic activity of CT leads to the profound secretory diarrhea that characterizes cholera [8]. There are currently two WHO prequalified, inactivated whole cell cholera vaccines commercially available, Dukoral and Shanchol. Since 2010, the WHO recommends the use of these vaccines [1], combined with other strategies, in cholera endemic areas, but to date this has been poorly implemented. A major reason for this is that the vaccines have significant immunological and practical limitations. Although the vaccines induce protective immunity, the efficacy is moderate and protection wanes rapidly, with poor protective efficacy in children [9-11]. In contrast, natural infection with *V. cholerae* induces 90-100% protection against re-infection, for up to ten years [12-14]. **Yet it remains poorly understood why infection confers long-lived protection and current vaccines do not.** A live attenuated cholera vaccine, Vaxchora, was approved in the US by the FDA [15]. In contrast to the inactivated whole cell vaccines, this novel vaccine only requires a single dose, making it more practical for travelers to cholera affected areas. In a human challenge study, a protective efficacy of 90% at day 10 and 80% at day 90 was demonstrated [16]. Interestingly, the 4 out of 33 volunteers that had measureable disease after challenge, displayed markedly less diarrhea, and shed three logs less bacteria in stool, arguing that they were partially protected. This is an important development, as with the ever-expanding travel by the population of developed countries, exposure to this severe human pathogen in one of the 69 cholera-endemic countries in Africa, Asia and the Caribbean is likely to increase. Finally, it is currently unknown if this vaccine would provide more long-lived protection than that afforded by the inactivated whole killed vaccines that show little protection already two years after vaccination.

Both live attenuated and cholera vaccines induce early antibody and plasmablast responses that are similar in magnitude to that of natural infection [14, 17-21]. However, the magnitude of the plasmablast response does not necessarily correlate with the induction or maintenance of long-term protection, at least in endemic areas [18, 22], suggesting that there is a need to better

understand these early immune responses and define what critical parameters predict a productive B cell response to cholera. We hypothesize that there are critical aspects of the acute plasmablast response induced by *V. cholerae* infection, in terms of homing potential to the intestinal mucosa and immunoglobulin isotype, repertoire and antigenic specificity/functional characteristics that dictate the protective efficacy and the duration of humoral immune responses, both systemically and in the intestinal mucosa.

V. cholerae as a model system to understand mucosal humoral immunity in humans.

Understanding human mucosal immunity and regulation of homing to mucosal tissues is of key importance, not only for *V. cholerae*, but for many other mucosal infections, such as influenza and HIV. For example, the discovery of broadly neutralizing monoclonal antibodies (mAb) against HIV [23], underscores the importance of clinical studies aimed at understanding humoral immunity at the mucosal barrier. It is necessary to understand mechanisms that determine mucosal homing and long-term survival of plasmacells in this compartment. Although animal models are essential to understand many mechanistic aspects of immunity, cholera is not recapitulated well in any model tested to date. Thus, the most informative approach is to study this pathogen directly in humans. In this proposal, we demonstrate that the study of cholera in humans offers a strong platform for understanding the induction and longevity of humoral immunity, against a pathogen of great importance for human health. In addition, while an infectious episode provides up to ten years of protection from infection, serum antibody titers rapidly wane to undetectable levels, underscoring the importance of studying mucosal immune responses at the site of action for protective immunity against cholera.

Over the last decade we have worked closely with our collaborators at MGH in Boston and at ICDDR'b in Bangladesh, to characterize acute systemic and mucosal B cell responses in *V. cholerae* infected patients in a cholera-endemic area in Bangladesh [24-26]. Our colleagues there have studied both blood borne [24, 26] and mucosal [20] (EGD) immune responses to both natural infection and against other, non-live vaccines. The studies proposed herein will expand and complement those studies and allow the direct comparison of infection driven immune responses in an endemic and a naïve setting.

In this study, we attempt to better understand the immune responses to the live-attenuated cholera vaccine (Vaxchora) in healthy naïve subjects. Single cell expression cloning will generate a panel of monoclonal antibodies from these patients to further dissect the antibody responses induced by this vaccine. In addition to providing insight into the biology of vaccine induced immune responses, this analysis may also generate reagents with potential diagnostic or even therapeutic potential. Finally, we attempt to better understand the mucosal immune response to the live-attenuated cholera vaccine (Vaxchora) in a subset of subjects.

1.2 Scientific Rationale

The immune response to cholera varies between natural infection and vaccination in terms of magnitude, quality and longevity. Here we attempt to better understand the immune response to cholera vaccination in healthy subjects who are naïve to cholera vaccination and/or infection. As protection against *V. cholerae* is thought to occur at the mucosal surface in the small intestine, we propose to analyze local, mucosal immunity induced by vaccination with the live attenuated cholera vaccine, Vaxchora. This analysis will provide key insight into the dynamics of protective immunity against cholera, and also significantly enhance our understanding of mucosal immunity in general, which is of importance for many other mucosal infections, such as rotavirus, shigella, and HIV infections.

1.3 Potential Risks and Benefits

The study utilizes an FDA-approved live cholera vaccine, Vaxchora. See package insert for full risks and benefits of the vaccine [27].

1.3.1 Potential Risks

The potential risks to all subjects are those associated with oral administration of the live cholera vaccine, possible reactions to the vaccine, and with having blood drawn.

The potential risks of receiving the live cholera vaccine include but are not limited to: tiredness (30%), headache (28%), abdominal pain (18%), nausea/vomiting (17%), lack of appetite (16%), diarrhea (4%), and fever (0.6%) [28]. If any participant develops severe watery diarrhea we will clinically assess the patient and facilitate access to treatment

Clinical trials found no related serious adverse reactions to the Vaxchora vaccine. Rarely, a subject may experience an allergic reaction, which produces rash, hives, or difficulty breathing. Vaccine products have been shown to be shed in stool for at least one week following administration, posing a potential risk. Subjects will be instructed to be diligent with hand washing and avoid contact with infants and immunosuppressed patients as per the vaccine package insert.

Blood sample collection involves transient discomfort and may cause fainting, which is managed by having the subject lie down prior. The blood draw site may bruise, and this can be ameliorated by holding pressure to this site following the blood draw. The sites of blood draw are potential sites of infection, but this risk is made very unlikely by the use of sterile technique.

For the subset of patients (n=30) for which an upper endoscopy biopsy (EGD) is performed, additional risks involve those associated with the EGD procedure. Risks of the EGD procedure include complications related to: sedation, endoscopy, and the biopsy extraction. In a large survey from 1974 that was based on 200,000 upper endoscopies, the overall complication rate was 0.13%, and the mortality rate was 0.004%. Subsequent studies have estimated

complication rates of 0.15% overall and 0.0002% for diagnostic endoscopy without therapeutic maneuvers [29-32]. The risk for the healthy cohort proposed herein are likely less, as the numbers above include patients with advanced age, cardiopulmonary disease, anemia or obesity. Since our cohort is a healthy patient population, we expect our complication rates to be lower.

The most frequent and serious complications of procedural sedation are cardiopulmonary, with risk factors being: advanced age, underlying comorbid illness (especially pulmonary disease), sleep apnea, obesity, anemia, and dementia. The frequency of cardiopulmonary events is associated with increasing American Society of Anesthesiologists scores. Some adverse events due to oversedation include: aspiration, hypoventilation, hypotension, hypoxemia, airway obstruction, vasovagal episodes, and arrhythmias. The overall incidence of cardiopulmonary complications is low. In a prospective survey of 14,149 upper endoscopies and a retrospective study of 21,011 endoscopic procedures, the rates of early cardiopulmonary events were 2 to 5.4 per 1000 cases and mortality rates were 0.3 to 0.5 per 1000 cases, including cases of pneumonia, pulmonary embolism, aspiration, and myocardial infarct [33, 34].

Bleeding rarely occurs following diagnostic upper endoscopy. While the risk may be increased in patients with thrombocytopenia or coagulopathies, diagnostic upper endoscopy is generally thought to be safe in patients with platelet counts as low as 20,000 [32]. The risk is increased with use of anticoagulants and antiplatelet medications.

Upper endoscopy is associated with perforation of the esophagus, stomach and small bowel. It is more common when therapeutic maneuvers are carried out and in patients with esophageal diverticula. The estimated risk of esophageal perforation varies with the procedure being performed [35].

- Diagnostic endoscopy with a flexible endoscope: 0.03%
- Diagnostic endoscopy with a rigid endoscope: 0.11%
- Stricture dilation: 0.09 to 2.2%
- Sclerotherapy: 1 to 5%
- Pneumatic dilation for achalasia: 2 to 6%

The risk of infection related to gastrointestinal endoscopy is low, though there have been cases of hepatitis B, hepatitis C, and bacterial transmission related to breaches in protocols for proper endoscope disinfection, including an outbreak of carbapenem-resistant Enterobacteriaceae associated with improper processing of side-viewing duodenoscopes [36].

1.3.2 Known Potential Benefits

While individuals are generally not at risk for acquiring cholera in the United States, the vaccine can offer protection to subjects if traveling to endemic countries, where individuals who receive this vaccine are likely to receive some level of protection from future *V. cholerae* exposure. The benefit for the study is predominantly scientific, allowing a better understanding of the immune response, in both the blood and in the mucosal tissues, to this particular vaccine.

2 OBJECTIVES

2.1 Study Objectives

Primary:

- To evaluate the antibody response to the cholera vaccine in healthy subjects.

Secondary:

- To evaluate B cell responses in healthy subjects receiving cholera vaccine.
- To evaluate the safety and reactogenicity in healthy subjects receiving cholera vaccine.

Exploratory:

- To evaluate mucosal cell responses in a subset of the healthy subjects receiving cholera vaccine.

2.2 Study Outcome Measures

Primary:

- Level of antibody titers at day 1 (pre-vaccination) and day 29 in serum.

Secondary:

- Levels of plasmablasts at days 1, 8 and 29
- Levels of activated B cells at days 1, 8 and 29
- Levels of memory B cells at days 1 and 29 .
- Correlation between antibody titers and the level of plasmablasts, activated B cells, and memory B cells.
- Production and characterization of monoclonal antibodies at day 8 against *V. cholerae* in a subset of subjects.
- Solicited and unsolicited adverse events in healthy subjects receiving cholera vaccine at day 8 and day 29 respectively.

- Serious adverse events in healthy subjects receiving cholera vaccine for the duration of the study

Exploratory:

- Levels of plasmacells, activated B cells and T cells in small intestinal biopsy samples at day 29 (n=15) or day 90 (n=5).
- Correlation between systemic and mucosal immune responses.
- Production and characterization of monoclonal antibodies against *V. cholerae* from a protected mucosal site.
- Levels of antibody titers at days 90 and 365.
- Levels of plasmablasts at days 11 and 15 in a subset of subjects.
- Levels of activated B cells at days 11 and 15 in a subset of subjects.
- Levels of T cells at days 1 and 29 in a subset of subjects.

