3 STUDY DESIGN

This study will be a prospective study, with 50 subjects total, who are between ages 18 and 49 years of age, in good health and meet all eligibility criteria. Each subject will make a total of 7 visits to the Hope Clinic. Subjects will be recruited from the Atlanta metro area. (See appendix). 30 of the subjects will also have two different visits at the GI suite during which small intestinal biopsies will be obtained: one at screening (-45 to -7 days) and the other post vaccination (Group 1 at Day 29 -7 days/ +14 days and Group 2 at day 90 +14 days) by EGD, and will have an additional follow-up phone call 7 days after the procedure. Subjects will be recruited from the Atlanta metro area.

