6.2 Follow-up and Final Visits

6.2.1 Visit 02 Day 08 Visit 03 Day 11, Visit 04 Day 15

Interim medical history and targeted physical exam, if necessary, will be conducted.

Medications taken during the interim from the previous visit and any adverse or serious adverse events will be documented on the appropriate study form.

Vital signs, including pulse rate, blood pressure, and oral temperature will be measured and documented on the appropriate study form-

Blood will be collected for immunogenicity analysis.

A review of the memory aid will be done at Visit 02.

Certain follow up visits (D11 and D15) will not be required by PI discretion.

6.2.2 Visit 05 Day 29

Interim medical history and targeted physical exam, if necessary, will be conducted.

Medications taken during the interim from the previous visit and any adverse or serious adverse events will be documented on the appropriate study form.

Vital signs, including pulse rate, blood pressure, and oral temperature will be measured and documented on the appropriate study form.

Blood will be collected for immunogenicity analysis.

Group 1 (n=15): a small intestinal biopsy using esophagogastroduodenoscopy will be performed by a gastrointestinal specialist at Emory GI suite. Visit will take 4 hours. The window for this visit is – 7 days/ + 14 days

6.2.3 Visit 06 Day 90

Interim medical history and targeted physical exam, if necessary, will be conducted.

Any serious adverse event will be documented on the appropriate study form.

Vital signs, including pulse rate, blood pressure, and oral temperature will be measured and documented on the appropriate study form-

Blood will be collected for immunogenicity analysis

Group 2 (n=5): a small intestinal biopsy using esophagogastroduodenoscopy will be performed by a gastrointestinal specialist at Emory GI suite. Visit will take 4 hours. The window for this visit is + 14 days. Visit 05a (EGD +7 days) and Visit 06a (EGD day+7 days)

Group 1 and 2: a follow-up phone call is to be made 7 days post-procedure to assess for any adverse events from the procedure. Visit 07 Day 365

Interim medical history and targeted physical exam, if necessary, will be conducted.

Any serious adverse event will be documented on the appropriate study form.

Vital signs, including pulse rate, blood pressure, and oral temperature will be measured and documented on the appropriate study form.

Blood will be collected for immunogenicity analysis

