6.3 Early Termination Visit (if needed)

The following will be performed at any early termination visit, if necessary, for subjects who withdraw or who are withdrawn from the study:

Interim medical history and targeted physical exam, if necessary, will be conducted.

A review of the memory aid will be conducted (if visit occurs within 7 days of vaccination).

Medications taken during the interim from the previous visit will be documented on the appropriate study form (if prior to D29).

Vital signs, including pulse rate, blood pressure, and oral temperature will be measured and documented on the appropriate study form.

Any adverse (prior to D29) or serious adverse events will be documented on the appropriate study form.

Blood will be collected for immunogenicity analysis.

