Adverse events	X	X	X	X	X	X	X				
Serious adverse events	X	X	X	X	X	X	X	X	X	X	X

#Prior to study procedures

*Prior to study vaccination.

+Not required if done at the screening visit

%All current medications and medications taken within 30 days prior to day 1 of the study.

&Vital signs assessed on Day 1 (Visit 1) before the study vaccination will be considered as baseline.

\$Subjects must not eat or drink anything hot or cold, or smoke within 10 minutes prior to taking oral temperature.

() Targeted physical examination if indicated based on review of complete or interim medical history.

@Must be performed on all female subjects of childbearing potential within 24 hours prior to each study vaccination and results must be negative and known prior to each study vaccination.

*Complete medical history by interview of subjects to be obtained on Day 0 (Visit 01) prior to the first study vaccination and interim medical history by interview of subjects to be obtained at follow-up visits after study vaccination.

!Only for participants agreeing to EGD i.e. Group 1 and 2

= Group 1 (n=25) will undergo small intestinal biopsy on D29 and Group 2 (n=5) subjects will undergo small intestinal biopsy at D90.

^Follow-up phone call post small intestinal biopsies via EGD.

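### Unsolicited adverse events are a Day 29 endpoint, but non-serious events are recorded only up to V05, which Appendix A allows from Day 22 to Day 43, and no onset cut-off is stated

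*Combined protocol and SAP*

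**What the plan says.** - **Endpoint.** Section 2.2 (secondary) lists "Solicited and unsolicited adverse events in healthy subjects receiving cholera vaccine at day 8 and day 29 respectively". Taken in order, solicited events go with Day 8 and unsolicited events with Day 29.
- **Where recording stops.** The non-serious row in Appendix A reads "Adverse events X X X X X X X". The seven marks run from Screen to V05; V05a, V06, V06a and V07 have none.
- **When V05 takes place.** The V05 column header in Appendix A carries a window of minus 7 to plus 14 days around Day 29, with no restriction to a group. In Section 3 the same window is tied to the biopsy: "Group 1 at Day 29 -7 days/ +14 days". Section 6.2.2 also states it straight after the Group 1 endoscopy.
- **What V05 records.** Under Section 6.2.2, "any adverse or serious adverse events will be documented on the appropriate study form". No limit on onset date is given.
- **What later contacts record.** At V06 and V07, "Any serious adverse event will be documented on the appropriate study form". For Groups 1 and 2, "a follow-up phone call is to be made 7 days post-procedure to assess for any adverse events from the procedure". Medical history is marked at all of these later contacts in Appendix A.
- **Early termination.** Section 6.3 says "Any adverse (prior to D29) or serious adverse events will be documented on the appropriate study form".
- **Analysis.** Section 7 plans descriptive statistics for the immune responses. It gives no adverse event window and no adjustment for length of follow-up.

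**The concern.** A visit window is harmless for an assay time point. Here the V05 date also ends the period in which non-serious events are recorded, so the booking decides which events reach the data. A non-serious event on Day 27 is recorded if the subject attends on Day 29, but has no scheduled place to be recorded if the subject attended on Day 22. An event on Day 35 is recorded only if V05 is late, and nothing says whether it then counts towards Day 29.

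The study has one arm, so no control group shares the unequal follow-up. A percentage labelled Day 29 could rest on different observation periods in different subjects. The late tail may also differ in kind: exclusion criterion 8 rules out plans for other vaccines only up to Day 29, so a late V05 could bring in reactions to a non-study vaccine. Non-serious events missed after an early visit are hard to recover reliably two months later at V06.

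**Working it through.** The plan gives no figure to reproduce. The check is day arithmetic, followed by an illustration on assumed risks.

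**Inputs.** Vaccination on Day 1 (Section 6.1.3); endpoint at Day 29 (Section 2.2); V05 window minus 7 to plus 14 days and last non-serious mark at V05 (Appendix A); V05a call 7 days after the endoscopy (Section 6.2).

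**Length of collection**
1. Earliest V05: 29 − 7 = Day 22, which is 22 − 1 = 21 days after vaccination.
2. Nominal V05: 29 − 1 = 28 days after vaccination.
3. Latest V05: 29 + 14 = Day 43, which is 43 − 1 = 42 days after vaccination.
4. Ratio of the extremes: 42/21 = 2.0.
5. Gap after a Day 22 visit: Days 23 to 29, 7 of 28 days, or 25%.
6. Excess after a Day 43 visit: Days 30 to 43, 14 days, or 14/28 = 50% more.
7. If the Day 29 label is applied as an onset cut, the excess goes but the gap stays: 28/21 = 1.33.

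**Can a later contact close the gap?** The earliest Group 1 endoscopy is Day 22, so the earliest V05a call is 22 + 7 = Day 29. That call is well timed, but Section 6.2 limits it to events from the procedure. V06 reaches everyone, but only serious events are to be recorded there.

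**Illustration (assumed, not from the documents).** Take a constant hazard and a 28-day risk p of at least one event. The risk over t days is 1 − (1 − p)^(t/28).

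| Assumed 28-day risk | 21 days (V05 on Day 22) | 42 days (V05 on Day 43, all events counted) |
|---|---|---|
| 10% | 7.6% | 14.6% |
| 20% | 15.4% | 28.4% |
| 30% | 23.5% | 41.4% |

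These are extremes in which every subject attends on the same day. A mixed cohort moves less. With p = 20%, an onset cut at Day 29, and an assumed quarter of subjects seen on Day 22 with the rest on Day 29 or later, the expected figure is 0.25 × 15.4% + 0.75 × 20% = 18.9%.

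**The case against.** The strongest reply is that this is a wording gap with small consequences. Its parts deserve separate answers.

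- **Subjects are asked later.** A reader might infer that someone seen on Day 22 is never asked about Days 23 to 29. The documents do not support that: medical history is marked at V05a and V06, and Section 6.1.3 tells subjects to contact the clinic about concerning reactions. What stands is narrower: no scheduled contact after V05 is set to record a non-serious event unrelated to the endoscopy.
- **The window may be for Group 1 only.** A reader might infer from Appendix A that it covers every subject. Sections 3 and 6.2.2 tie it to the Group 1 biopsy, so this is unsettled. On the narrow reading the spread remains within Group 1 (15 subjects in Section 6.2.2, 25 in the Appendix A footnote), and the gap falls on subjects who already receive a call on or after Day 29.
- **The two-fold spread depends on the analysis.** Recording an event at a late visit does not mean tabulating it under Day 29. This is fair. With an onset cut the ratio is 1.33 and only the early gap remains, but the plan states no such cut.
- **Section 6.3 may not be a different rule.** The neighbouring lines there depend on when the visit occurs, so its Day 29 limit may mean only that events are collected if termination comes before Day 29. It can be read either way, and a contradiction cannot be claimed.
- **Other safety results are sound.** It would be too strong to call the unsolicited percentage the safety result. Solicited events at Day 8 do not depend on V05, and Section 2.2 also lists "Serious adverse events in healthy subjects receiving cholera vaccine for the duration of the study".

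**Conclusion.** The point holds in a limited form. If Appendix A is followed as written, recording of non-serious unsolicited events lasts from 21 to 42 days after vaccination, with up to 7 of 28 days uncovered after an early V05 and up to 14 additional days after a late one. The ratio is 2.0 at the extremes and 1.33 under an onset cut at Day 29.

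This rests on reading the Appendix A window as covering all of V05, which Sections 3 and 6.2.2 leave open, and on V05 having no onset limit, which Section 6.2.2 supports by giving none. A reader might infer that the reported percentage will be wrong by a factor of two. The documents do not support that: visit dates and event rates are unknown, and the percentages under the working are illustrations.

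The consequence is confined to the non-serious unsolicited proportion and its comparability with a fixed 28-day figure. No test or decision rule depends on it. A fixed period looks intended, since Section 6.1 documents medications for 28 days after vaccination. The change is worth making because it is cheap and affects which events are captured and counted.

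**What to change.** 1. In Section 2.2, define the outcome as unsolicited adverse events with onset from vaccination on Day 1 through Day 29, for all subjects.
2. In Section 6.2.2 and Appendix A, say that if V05 falls before Day 29, adverse event collection is completed through Day 29 by a brief phone contact. For Group 1, broaden the question asked at the existing V05a call, which never falls before Day 29.
3. Record events with onset after Day 29, but list them separately from the Day 29 tabulation.
4. Reconcile Sections 3 and 6.2.2 with Appendix A on whether the V05 window covers all subjects or only the Group 1 endoscopy.
5. Reword Section 6.3 so that its Day 29 limit is plainly the same onset rule.

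An onset cut without step 2 is not enough, because early attenders would still have 21 days against 28.

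**Cost.** A few sentences and some short calls. Only subjects outside Group 1 with an early V05 need a new call. Even if all of them attended early, that is at most 50 − 15 = 35 calls, or 50 − 25 = 25 with the Appendix A group size.

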4 STUDY POPULATION

4.1 Selection of the Study Population

The target sample size will be 50 subjects who will receive the Vaxchora live cholera vaccine, of whom 30 will undergo two procedures for small intestinal biopsies (6-12 biopsies per EGD procedure in total): one at screening and the other post vaccination (Group 1 at Day 29 and Group 2 at day 90) by an EGD. With the exception of the inclusion/exclusion criteria, there will be no intentional recruitment of particular ethnic or racial groups. Subjects will be screened for eligibility according to the inclusion/exclusion criteria by history. Informed consent will be obtained for study participation.

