7 STATISTICAL CONSIDERATIONS

The goal of this study is to study the immune responses to the live attenuated cholera vaccine Vaxchora in healthy, cholera infection/vaccination naïve subjects by analysis of the blood and mucosal tissue samples from the small intestine.

Our aim is to include a total of 50 participants who will receive the live attenuated oral cholera vaccine (Vaxchora), of which 30 participants will undergo 2 procedures for small intestinal biopsy via EGD by a gastrointestinal specialist at Emory University Hospital.

The biostatistician will perform descriptive statistics to describe the immune responses to cholera vaccine. As a faculty in the Department of Pediatrics, [name] has access to an excellent Statistical Core that is provided free of charge.

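### Group 1 (Day 29 biopsy) is 15 subjects in the endpoint and visit text but 25 in Appendix A, so the EGD subset is 20 or 30 depending on the section read

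*Combined protocol and SAP*

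**What the plan says.** The number of subjects having small intestinal biopsies by upper endoscopy (EGD) is stated in two ways.

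**As a total of 30:**
- Section 1.3.1 (Potential Risks): "For the subset of patients (n=30) for which an upper endoscopy biopsy (EGD) is performed".
- Section 3 (Study Design): "30 of the subjects will also have two different visits at the GI suite during which small intestinal biopsies will be obtained". The section puts one visit at screening and the other after vaccination.
- Section 4.1 (Selection of the Study Population): "of whom 30 will undergo two procedures for small intestinal biopsies".
- Section 7 (Statistical Considerations): "of which 30 participants will undergo 2 procedures for small intestinal biopsy via EGD".

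**As two group sizes:**
- Section 2.2 (Study Outcome Measures, exploratory): "Levels of plasmacells, activated B cells and T cells in small intestinal biopsy samples at day 29 (n=15) or day 90 (n=5". The Protocol Summary carries the same endpoint with the same numbers.
- Section 6.2.2 (Visit 05, Day 29): "Group 1 (n=15): a small intestinal biopsy using esophagogastroduodenoscopy will be performed". Section 6.2.3 (Visit 06, Day 90) gives Group 2 as 5.
- Appendix A (Study Schedule), footnote: "Group 1 (n=25) will undergo small intestinal biopsy on D29 and Group 2 (n=5) subjects will undergo small intestinal biopsy at D90".

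Section 7 plans descriptive statistics only. It gives no split between the groups, no precision target, and no alpha, power or effect size.

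**The concern.** A total and its parts should agree, and here they agree only if Appendix A is read and Sections 2.2 and 6.2.2 are not. Two things depend on the answer.

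The first is exposure. The figure sets how many healthy volunteers have two EGDs. Section 1.3.1 lists risks from sedation, endoscopy and biopsy, and Section 1.3.2 describes the study's benefit as mainly scientific. Anyone weighing that burden, including the IRB, needs a single number.

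The second is the sample size of the exploratory biopsy endpoint, the only mucosal endpoint that carries an n. The planned correlation of systemic with mucosal responses has no stated n, but it cannot use more subjects than are biopsied. Section 7 does not give the split, so it cannot settle the matter.

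**Working it through.** **Inputs**

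| Place | Group 1 (Day 29) | Group 2 (Day 90) | Total |
|---|---|---|---|
| Protocol Summary; Section 2.2 | 15 | 5 | not stated |
| Sections 6.2.2 and 6.2.3 | 15 | 5 | not stated |
| Appendix A footnote | 25 | 5 | not stated |
| Sections 1.3.1, 3, 4.1, 7 | not stated | not stated | 30 |

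**Step 1. Reproduce the stated total of 30.**
- Endpoint and visit text: 15 + 5 = 20. This does not reproduce 30.
- Appendix A: 25 + 5 = 30. This does.

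**Step 2. Locate the conflict.** Group 2 is 5 in every place that sizes it. Group 1 is 15 in the Protocol Summary and Sections 2.2 and 6.2.2, and 25 in Appendix A. The whole difference is therefore in Group 1: 25 − 15 = 10 = 30 − 20.

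**Step 3. Size in subjects and procedures.**
- 10 of 30 subjects is 33% of the stated subset.
- Two EGDs per subject: 2 × 20 = 40, or 2 × 30 = 60. The difference is 20 procedures.
- As a share of the 50 enrolled: 20/50 = 40%, or 30/50 = 60%.

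**Step 4. Effect on precision (illustrative).** The plan gives no SD, so the half-width of a 95% t-interval for a mean change is expressed in SD units: h = t(0.975, n − 1)/√n.

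| Set | n | t/√n | h (SD units) |
|---|---|---|---|
| Group 1, endpoint and visit text | 15 | 2.145/3.873 | 0.55 |
| Group 1, Appendix A | 25 | 2.064/5.000 | 0.41 |
| Both groups, 15 + 5 | 20 | 2.093/4.472 | 0.47 |
| Both groups, 25 + 5 | 30 | 2.045/5.477 | 0.37 |

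The Group 1 interval is about a third wider at 15 than at 25 (0.554/0.413 = 1.34). Group 2 is the same under either reading, so its precision does not bear on this point.

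**The case against.** **Perhaps 30 are biopsied and only 20 are analysed.** This would rescue Section 2.2, which describes an endpoint. It does not rescue Section 6.2.2, which gives 15 as the number in Group 1 who have the Day 29 procedure. Appendix A gives 25 for the same group, procedure and day. Nor do the documents mention an allowance for dropout or failed samples that would take 25 to 15.

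**Perhaps there is a further biopsied group of 10.** None is described. Sections 3 and 4.1 assign the post-vaccination EGD to Groups 1 and 2 only.

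**The endpoints are exploratory and the analysis is descriptive.** This stands. No hypothesis test, alpha or power rests on the biopsy n, and the statistical consequence alone would be modest. The stronger ground is that the number of volunteers having an invasive procedure twice is stated inconsistently.

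**Stronger readings that a reader might infer, and that the documents do not support:**
- *Ten subjects would have a screening EGD with no post-vaccination pair.* Sections 3, 4.1 and 7 give all 30 two procedures. Section 6.1.1 and Appendix A confine the screening EGD to Groups 1 and 2, and each of those groups has an assigned second EGD. The text yields 20 pairs or 30 pairs, not 30 first biopsies and 20 second ones.
- *Three competing totals.* There are two. Appendix A agrees with 30.
- *A change in the smallest significant correlation.* That presupposes a test and a type of correlation that the plan does not specify.

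**Conclusion.** The concern holds. Current operative text gives Group 1 two sizes for the same Day 29 procedure, and so gives the EGD subset two sizes, 20 and 30. The difference is 10 subjects, or 40 against 60 EGDs. On precision, the illustrative half-width for a Group 1 mean change is 0.55 SD or 0.41 SD. Those two figures assume one paired change per subject, complete data and a t-interval, none of which the plan sets out. The counts rest only on addition and on two EGDs per subject, as Sections 3, 4.1 and 7 state.

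The conflict is limited to the biopsy subset. The primary endpoint, serum antibody titers at Days 1 and 29, does not depend on the biopsy split.

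The documents do not show which Group 1 size is intended. That 25 + 5 matches the stated total does not settle it, because 15 appears in three separate places.

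**What to change.** Reconcile the text so that one total and one split appear in the Protocol Summary, Sections 1.3.1, 2.2, 3, 4.1, 6.2.2, 6.2.3 and 7, and the Appendix A footnote. The edits depend on what the investigators intended:

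- If the total is 30 and Group 2 is 5, Group 1 must read 25 in the Protocol Summary and in Sections 2.2 and 6.2.2.
- If Group 1 is 15 and Group 2 is 5, the total must read 20 in Sections 1.3.1, 3, 4.1 and 7, and the Appendix A footnote must read 15 for Group 1.

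Stating the split in Sections 3 and 7 as well as the total would let a reader check the sum in one place. The cost is wording in a protocol amendment. No new data or analysis is needed.
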